Protocol

1. Project Title:

Nonpharmacologic Management of Challenging Behaviors in Veterans with Dementia

2. Investigator(s):

[name], OTR, Ph.D., Principal Investigator
[name], B.A., Coordinator
W. [name]., Other (Economist/Statistician)
[name] (Statistician)
[name], M.S., MOT, Other (Interviewer)
[name], MOT, Other (Interventionist)
[name], Other (WOC)
[name].

3. Abstract:

Over 5 million Americans have Alzheimer's disease or related dementias, a progressive and irreversible neurodegenerative syndrome, with prevalence rates expected to reach close to 16 million individuals by 2050. As populations age worldwide, dementia will increase dramatically and reach epidemic proportions. Among Veterans 65 and older, prevalence rates are similar to the population at-large with 7.3% having dementia across all races, except for African-Americans for whom the rate is 50% higher. Prevalence rates across VISNs range from 5.8 to 9.4% with dementia associated with substantially higher Inpatient and outpatient service utilization relative to other VA patients.

A hallmark of dementia is neuropsychiatric symptoms (NPS) which include agitation, apathy, depression, mood lability, and aggressiveness. NPS are associated with increased health care costs, and reduced quality of life and daily functioning, heightened family caregiver burden, and nursing home placement. Standard care typically involves pharmacologic agents, but these are at best modestly effective, carry serious risks including mortality, and do not address behavioral symptoms families themselves consider most distressful or that prompt nursing home placement. Given the devastating effects of the disease and that a cure is not imminent, medical organizations nationally and internationally including the VA have urged for the development and testing of new approaches to manage NPS.

This proposed study addresses this call by testing the efficacy of a transformative patient-centric intervention designed to reduce the burden of NPS in Veterans with dementia who live at home with family caregivers. The innovative intervention, the Tailored Activity Program (TAP-VA), involves 8 sessions over 4 months in Veterans' homes. An occupational therapist conducts a systematic assessment to identify a Veteran's preserved capabilities and deficit areas, and previous roles, habits and interests from which to develop and introduce activities tailored to the Veteran's profile. Family caregivers are then trained to incorporate tailored activities into daily care routines. The intervention was pilot tested in an NIMH funded study with 60 community-living individuals with dementia. Findings from this pilot showed statistically significant and clinically meaningful reductions in NPS, specifically agitation and less time being on "duty" by family caregivers. Results of this pilot phase support moving forward with a full-scale Phase III efficacy trial. We plan to test TAP-VA in a randomized two-group parallel design in which 160 racially and ethnically diverse Veterans with dementia and their family caregivers (dyads) will be randomly assigned to receive TAP-VA or an attention control group. All dyads will be evaluated at baseline and 4-months (main trial endpoint), and then reassessed at 8-months to evaluate long-term treatment effects (baseline to 8 months), including continued activity use, caregiver well-being, and costs.

4. Background:

Over 5 million Americans have Alzheimer's disease or related dementias, a progressive and irreversible neurodegenerative syndrome, with prevalence rates expected to reach close to 16 million individuals by 2050. As populations age worldwide, dementia will increase dramatically and reach epidemic proportions. Among Veterans 65 and older, prevalence rates are similar to the population at-large with 7.3% having dementia across all races, except for African-Americans for whom the rate is 50% higher. Prevalence rates across VISNs range from 5.8 to 9.4% with dementia associated with substantially higher Inpatient and outpatient service utilization relative to other VA patients.

A hallmark of dementia is neuropsychiatric symptoms (NPS) which include agitation, apathy, depression, mood lability, and aggressiveness. NPS are associated with increased health care costs, and reduced quality of life and daily functioning, heightened family caregiver burden, and nursing home placement.^{4,5} Standard care typically involves pharmacologic agents, but these are at best modestly effective, carry serious risks including mortality, and do not address behavioral symptoms families themselves consider most distressful or that prompt nursing home placement. Given the devastating effects of the disease and that a cure is not imminent, medical organizations nationally and internationally including the VA have urged for the development and testing of new approaches to manage NPS.

5. Specific Aims:

Our primary study aim concerns the Veteran with dementia and tests the immediate effect of TAP-VA at 4-months on NPS. Our *hypothesis* is that Veterans with dementia who receive TAP-VA will manifest lower total scores on the Neuropsychiatric Inventory (NPI), which assesses frequency and severity of 12 common neuropsychiatric symptoms, compared to Veterans assigned to an attention control group. We also propose **four secondary aims**. These are to: 1) Test the long-term effects of TAP-VA at 8-months on quality of life and neuropsychiatric behaviors of Veterans with dementia. *Hypothesis*: Veterans receiving TAP-VA will manifest higher quality of life and lower total NPI scores over time (baseline to 8-months) in comparison to Veterans in the attention control group; 2) Test the immediate effects of TAP-VA at 4-months and long-term effects at 8-months on caregiver burden, skill acquisition, efficacy using activities, and time spent providing care. *Hypotheses*: Caregivers receiving TAP-VA will report reduced burden, enhanced skills and efficacy using activities, and less time providing care compared to the control group at 4 and 8-months; 3) Examine whether caregivers receiving TAP-VA are using activities at 8 months; and 4) Examine whether TAP-VA results in reduced VHA health care use and costs for Veterans with dementia and their caregivers. Results from these secondary aims will provide further evidence of treatment efficacy, identify whether booster sessions are necessary, and inform dissemination efforts and translation of TAP-VA system-wide.

Our long-term objective, if proven efficacious, is to integrate TAP-VA into standard care practices within the VHA system as the first treatment choice to address NPS in Veterans with dementia living at home. This would transform the current paradigm of dementia care which relies on pharmacologic management.

[figure not shown]
6. Research Plan:

Overview: This study will test whether a targeted Veteran-centric intervention reduces NPS (NPI total score of frequency by severity) and, secondarily, whether it reduces burden by reducing time spent in care, and enhancing skill in family caregivers. We also seek to evaluate its cost savings in terms of health care utilization rates of both Veterans and family caregivers using a cost diary. We will enroll 160 Veterans with dementia whose caregivers report one or more NPS and are living at

home. Veterans with diagnosis codes 290.0, 290.2, 290.3, 331.2 (senile dementias), 290.4 (vascular dementia), 294.8 (dementia not otherwise specified), 331.0 (Alzheimer's disease), 331.1 (frontotemporal dementia), and 331.82 (Lewy body dementia) will be considered to have dementia diagnoses and eligible for study participation. Veterans with these diagnostic codes will be recruited from NF/SG VHS Geriatric Research, Education & Clinical Center (GRECC) and Geriatrics and Extended Care Service (GECS) outpatient services, including the Home Based Patient Care (HBPC) and Homemaker Home Health Aide program.

Eligible dyads will receive a baseline home interview (T1), and then be randomized to experimental (TAP-VA) or attention-control group conditions. Experimental dyads will receive up to 8 contacts with an occupational therapist (OT) interventionist over 4-months whereas caregivers in the attention control group will receive bi-monthly telephone contact (up to 8 contacts) in which education is provided and tailored to address unmet expressed informational needs of caregivers. Information concerning the value of activity and a list of activity ideas will also be provided. All dyads will be retested at 4-months from baseline (T2), main study endpoint, and 8-months from baseline (T3) at home to evaluate long-term effects. Interviewers will be masked to treatment assignment throughout the study (Figure 1). Each study component is described in more detail below.

**FIGURE 1
FLOW CHART OF STUDY DESIGN**

Eligibility Criteria: Inclusion Criteria for Veterans with dementia include: 1) English speaking; 2) diagnosed with dementia as above; 3) able to participate in at least two activities of daily living (ADLs - bathing, dressing, grooming, toileting, transferring from bed to chair); and 4) not currently participating in any other dementia-related intervention. If the Veteran with dementia is on any of four classes of psychotropic medications (antidepressant, benzodiazepines, antipsychotic, or anti-convulsant) or an anti-dementia medication (memantine or a cholinesterase inhibitor), we will require that he/she have been on a stable dose for 60 days prior to enrollment to minimize possible confounding effects of concomitant medications (the typical time frame used in clinical trials) and 5) 23 or less on the MMSE. Caregivers of Veterans must be: 1) English speaking, 2) self-identify as the primary member of the family caring (hands-on or supervision) for the Veteran and 21 years of age or older (male or female), Legal Authorized Representative (LAR), 3) living with the Veteran, 4) accessible by telephone to schedule interview, intervention sessions and follow-up interviews, 5) planning to live in area for 8 months (to reduce loss to follow-up), 6) indicate willingness to learn activity use, 7) report one or more NPS in the Veteran in the past month; and 8) not currently participating in any other caregiver-related intervention. Finally, we will require that caregivers taking a psychotropic medication (antidepressant, benzodiazepines, antipsychotic, or anti-convulsant) at time of telephone screen be on a stable dose of the medication for 60 days prior to enrollment. In the event more than one caregiver wishes to be involved in the study, the study team will obtain informed consent from each caregiver and will work with them as a caregiving unit.

Recruitment Procedures: Our recruitment and enrollment procedures primarily target the caregivers of VA patients in geriatric service programs that are directed by [name], co-investigator on this project. Services include Home Based Patient Care (HBPC) and the Homemaker Home Health Aide program. Our recruitment strategy is based on over 20 years experience with and success in enrolling families managing dementia in clinical trials. It will involve mailings to families identified through the VA services. The mailing will include a letter from the medical director of the service ([name]) explaining study procedures and inviting study participation and it will also include a descriptive flyer about the study. Caregivers will be directed to either contact the research team by telephone or to return a post card in a self-addressed and stamped envelope that indicates an interest in being contacted by the study team to learn about the study. Caregivers contacting the research team either way will be explained study procedures; and if interested, they will complete a brief telephone screen to determine eligibility. For caregivers eligible and willing to participate, a baseline interview will be conducted by a trained interviewer within 2 weeks of determination of eligibility, and prior to randomization to study group. At the time of the interview, the Mini-mental Status Examination (MMSE) will be administered to the Veteran. For Veterans with MMSE scores >23, a follow-up telephone call with their physician to confirm a dementia diagnosis will be obtained. Dyads eligible and willing following the baseline interview will be randomized (see data analytic considerations) to treatment or attention control. Caregivers who do not respond to the initial mailing will receive a second, duplicate mailing several months after the first mailing. Subsequent recruitment letters, including the flyer, will be sent to the following facilities in the NF/SGVHS study area:

1. Altrusa House, Gainesville
2. All Saints Daycare Center, Jacksonville

3. The Sunshine Center, St. Augustine
4. Blessed Trinity Adult Elder Care Home, Ocala
5. Tallahassee Memorial Rehabilitation Center, Tallahassee
6. Hope Adult Day Care, Inc., Jacksonville Beach
7. VA Social Work Service, NF/SGVHS
8. VA Mental Health Clinic, NF/SGVHS
9. Al'z Place, Gainesville
10. Brooks Rehabilitation Hospital, Jacksonville
11. Park of the Palms, Keystone Heights

These letters will request nursing staff and social workers to ask Veterans or their caregivers who might benefit from or be interested in this study to call the study team at the toll free number listed on the flyer.

Subject Accrual, Replacement Rule, Subject Attrition and Retention: *Subject Accrual:* Recruitment procedures will be implemented in month 6 of project year 01 and continue to month 3 of year 04 for a total of 33 months with close to 5 dyads enrolled per month. Based on our previous caregiver studies, the typical response rate from a targeted mailing to families is 10%; of responders, typically over 80% are eligible to participate in our studies that have similar enrollment criteria as that proposed for this trial. Thus, as shown in Table 1, even with one mailing from the two primary VA recruitment sources, we would be able to obtain our target sample size of 160 even when a conservative estimate of a 60% eligibility rate is applied. The numbers in the table were based on projections developed from actual new patients in each NF/SG VHS service over the past two years, with data provided by the GRECC. Thus, we do not anticipate difficulties obtaining the desired sample size dyads.

Techniques: The intervention is designed to tap into spared or residual abilities and provide an environment supportive of these abilities. The OTs select activities that build on preserved capabilities but do not tax areas of cognition that are most impaired (e.g., memory, new learning). In designing activities, OTs simplify activity and structure it to focus on single rather than multiple or complex tasks, thereby minimizing errors. The activity environment is set up to provide auditory or tactile cues to facilitate recall and guide initiation and sequencing. By grading activities to match the Veteran's capabilities, the OT minimizes demand that may heighten stress (e.g., high functioning individuals will be introduced to more goal-directed and multi-step activities, whereas lower functioning individuals will be introduced to activities that are based on repetitive motion (e.g., washing windows, folding towels) and integrate multi-sensory stimulation (e.g., soft music, objects pleasant to touch). Whereas previous activity interventions emphasized new learning, our approach does not, although it may entail some procedural learning if appropriate.

TAP provides caregivers with the requisite knowledge and skills to use activities. Caregivers are instructed in specific skills such as ways to simplify activities, the environment and their communication, and how to help the Veteran initiate and follow a sequence. The overall goal is to provide predictability, familiarity and structure in the daily life of Veteran and caregiver and establish a level of environmental stimulation appropriate to Veteran abilities. Three clinical elements are used to enhance caregiver receipt and enactment of intervention strategies: 1) the OT engages caregivers (vs being prescriptive), 2) the caregiver is provided repeated opportunities for practice and modification of techniques, and 3) the OT uses validation and actively demonstrates techniques within the context of their use. Caregivers are provided concrete knowledge as to what the Veteran is capable of doing (e.g., can grasp object such as a plate) and his/her specific limitations (e.g., needs verbal cueing to place dish in cabinet). With this knowledge, interventionists can help caregivers cognitively restructure their expectations, behavioral goals and reactions to the Veteran.

During treatment sessions, caregivers are taught to: 1) recognize capabilities and deficits, 2) translate capabilities into objective activity goals, and 3) generate specific steps to set up activities and help caregivers initiate/sequence.

7. Possible Discomforts and Risks:

This study involves the delivery of an online caregiving training and telephone support for CGs of elderly Veterans with dementia.

If a research staff member encounters a medical emergency over the telephone, we identify whether another individual is in the home, the person is put on hold and we call 911 immediately. If the situation occurs within the home, then the staff person calls 911 immediately, and stays with participant until help arrives. The PI is informed within 24 hours of the event. PI then contacts individual as a follow-up within two days. Research staff member completes alert form and provides to PI.

If a research staff person encounters a situation in which the person (Veteran or CG) threatens to hurt self immediately, then staff person stays with person (on phone or in home), calls 911 and stays with individual until help arrives. If the person (Veteran or caregiver) is determined to not be an immediate threat to self, then the person is actively encouraged to contact physician or contact is made for the person if they allow that. An agreement is obtained with the person that they will not hurt themselves. The research staff person also informs the person that a member of the research team will be contacting him/her shortly to follow-up. Immediately at the conclusion of the interview, the PI is notified of the situation. The PI contacts the person to obtain further information and encourages immediate action be taken (e.g., physician referral). PI consults about case within 24 hours of event and consultation with the team's geriatrician will occur to review next steps. Research staff person involved fills out Alert form and provides to PI.

If caregiver scores in the high depressed range on the CES-D (>15 on 10-item version) in an interview, the PI contacts the caregiver to inform them of their elevated score and that they should follow-up with their physician. Consultation by the team's geriatrician will be obtained if necessary. Research staff person involved completes Alert form and provides to PI.

Evidence of physical abuse is as follows:

- 1) Caregiver or Veteran with dementia states to research staff that abuse occurs;
- 2) or research staff observes physical evidence (black eye, black and blue marks on arms/legs)

Research staff member informs participant that a senior member of the research team will contact him/her later that day. Staff member informs PI immediately upon completion of interview or intervention session. PI (or designate) contacts participant to obtain further information. Participant is strongly encouraged to call his/her physician and/or Adult Protective Services (phone number will be provided). Based on the situation, the PI may notify Adult Protective Services and consult with team's geriatrician. PI (or designate) completes Alert form.

The DSMB will be responsible for reviewing the safety of study participants during the conduct of this study and provide recommendations to the research team on specific aspects of the research protocol as it pertains to safety, potential study alerts and adverse events. Specific responsibilities

of the DSMB will be to: a) provide an independent periodic review of recruitment and enrollment progress; b) review adverse events (AEs) including serious events and offer recommendations regarding the trial based on such observed events; c) serve in a consultative capacity to the research team regarding study procedures to address ethical dilemmas (e.g., reporting of abuse), safety of subjects in the trial, and appropriateness of all study procedures.

Composition of the DSMB: The DSMB will be an independent multi-disciplinary group consisting of biostatistical and research and clinical experts who collectively have experience in the treatment of depression, dementia and the environment, and the conduct and monitoring of randomized clinical trials that are community/home-based and nonpharmacologic. The 5-member board has no apparent conflict of interest with the study including financial, scientific or regulatory in nature. DSMB members are not employed by VHS and are not paid consultants on any related study of the principal investigator or that conducted by other members of the research team. DSMB members will be responsible for advising the principal investigator of any changes in their relationship and/or financial interests that occur during the course of the trial. The DSMB and PI will be responsible for deciding whether these changes create a conflict of interest. Any DSMB member who develops a conflict of interest during the course of the trial will be asked to resign from the DSMB and another person with similar areas of expertise will be sought. Otherwise, DSMB membership is to be for the duration of the trial.

DSMB Meetings, Documentation: The DSMB will have one face-to-face meeting prior to entering into the field for the trial and one tele-conference call each subsequent year unless the DSMB decides otherwise at its first organizational meeting. More frequent meetings or teleconferences may be held to review serious adverse events from the trial at the discretion of the DSMB. At the initial meeting in year 01 (anticipated to occur in month 3 prior to entry into the field), the DSMB will review all study procedures including data collection forms, intervention protocol and oversight plan. At this meeting, the DSMB will agree on whether there should be interim analyses of efficacy endpoints and, if so, the stopping rules and interim analysis plan that avoids potentially biasing the investigative team. Modifications to protocols based on the DSMB review will be made prior to entering the field. At subsequent conference calls, the DSMB will review the progress of the study (accrual rate, protocol deviations and interim study analyses if recommended) and make recommendations. A representative of the research team will keep minutes of these meetings. A copy of the minutes approved by the DSMB will be shared with the IRB -01. The minutes will include recommendations of the DSMB. Meetings of the DSMB will be open unless the DSMB requests otherwise. A closed meeting of the DSMB may be requested if it is deemed necessary to review efficacy data. The DSMB chair or his/her designate will take meeting notes of closed sessions.

Provision of Data for DSMB Review: Interim Analyses: We have elected to not consider interim analyses in this study due to the extended time for recruitment and the low likelihood of a sufficiently large effect that would make it possible to stop early. However, we will revisit this decision with the DSMB at its first organizational meeting.

8. Possible Benefits:

Participants may learn about dementia and may be able to apply that knowledge in their daily CG activities. A better understanding of the responsibilities and varied activities of CGs of elderly Veterans with dementia will further research on the Veteran CG role: responsibilities, benefits and value.

9. Conflict of Interest:

There is no conflict of interest for the investigators.

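### Could intervention contacts run past the 4-month main endpoint because the protocol does not say when the contact period starts?

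*Protocol*

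**What the plan says.** The Overview in section 6 of the protocol sets the order of events: "Eligible dyads will receive a baseline home interview (T1), and then be randomized to experimental (TAP-VA) or attention-control group conditions". Recruitment Procedures in the same section repeats it: "Dyads eligible and willing following the baseline interview will be randomized".

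On the treated arm, the Overview says: "Experimental dyads will receive up to 8 contacts with an occupational therapist (OT) interventionist over 4-months". The Abstract likewise gives eight sessions in four months. For the control arm, the Overview gives a pace and the same maximum number of telephone contacts, but no separate duration.

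The outcome visit is counted from baseline: "All dyads will be retested at 4-months from baseline (T2), main study endpoint". T3 follows at 8 months, also from baseline. Section 5 states that the primary aim "tests the immediate effect of TAP-VA at 4-months on NPS" and treats the 8-month results as long-term.

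For Veterans scoring above 23 on the MMSE at the baseline interview, Recruitment Procedures adds a step: "a follow-up telephone call with their physician to confirm a dementia diagnosis will be obtained".

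**The concern.** The assessment interval and the contact period have the same nominal length, four months, but only the first has a stated starting point. Contacts cannot start on the day the T2 clock starts unless randomization and the first visit happen at once. If the four months of contacts were counted from randomization or from the first visit, and ran in full, they would end as many days after T2 as they began after baseline.

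The stake would be the primary outcome. A dyad still receiving visits at T2 would have its NPI score taken in mid-programme, while the aim is the immediate effect of the programme. If the effect builds up with the number of contacts, that would shrink the observed difference. The physician call for higher MMSE scores has no stated time limit, so it looks like a source of such delay.

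**Working it through.** **Inputs.** T2 at 4 months from baseline; T3 at 8 months; up to 8 contacts; 4 months of TAP-VA contacts; control calls bi-monthly (all from the Overview in section 6). One month is taken as 365.25/12 = 30.44 days, so T2 falls on day 4 × 30.44 = 121.75.

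**The plan's own pace.** 8 contacts / 4 months = 2 per month. This agrees with bi-monthly read as twice a month. The other reading, one call every two months, would need 7 × 2 = 14 months for eight calls, well past T3, so it cannot be meant.

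**Latest first contact at that pace.** Eight contacts have seven gaps.

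- Gap: 30.44 / 2 = 15.22 days
- Contact 1 to contact 8: 7 × 15.22 = 106.5 days
- Room before T2: 121.75 − 106.5 = 15.2 days

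Contacts completed by T2, for waits chosen only as illustrations:

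| First contact (days after baseline) | Contacts by T2 |
|---|---|
| 0 to 15 | 8 |
| 16 to 30 | 7 |
| 31 to 45 | 6 |

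**How firm the 15 days is.** The bi-monthly pace is stated for control telephone calls. For the occupational therapist's contacts the protocol gives only the maximum and the duration. The room before T2 is 121.75 − 7 × gap:

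| Spacing of eight contacts | Room before T2 (days) |
|---|---|
| First to last over the full 4 months (17.4 days) | 0 |
| Twice a month (15.2 days) | 15.2 |
| Every 14 days | 23.8 |
| Every 10 days | 51.8 |
| Weekly | 72.8 |

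The limit therefore depends on an assumed spacing, and the protocol fixes none for this arm.

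**The passages side by side.** The Abstract places eight sessions in four months beside evaluation at baseline and at 4 months. Section 5 calls the 4-month result immediate and the 8-month result long-term. The Overview describes the contacts between its mention of T1 and its mention of T2. The two four-month spans are presented as one interval, and with the contacts counted from baseline, none falls after T2.

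**Evidence of delay.** The one step named between baseline and randomization is a telephone call to a physician. It concerns Veterans with an MMSE above 23, whereas Eligibility Criteria asks for "23 or less on the MMSE". Those two passages need reconciling, but that is a separate eligibility matter and does not show that first contacts come late.

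**Would a completion rule change the endpoint?** Take a 30-day wait at two contacts a month. Contact 7 falls on day 30 + 6 × 15.22 = 121.3, just before T2, and contact 8 on day 30 + 106.5 = 136.5. Requiring contacts to finish before T2 would cancel contact 8. The dyad would still have had seven contacts at T2, unless visits were placed closer together, which the protocol already permits.

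**The case for a change.** The strongest argument for the concern is that no sentence in the text shown gives the start of the contact period, limits the wait from baseline to first contact, or says contacts end before T2. The one time limit nearby, two weeks, runs from determination of eligibility to the baseline interview and does not cover this gap. When contacts occur relative to the outcome visit is study conduct and could not be left to an SAP. Late contacts would also shorten the contact-free stretch before T3: in the 30-day example it would be 243.5 − 136.5 = 107 days rather than about 122.

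The silence is real, and the arithmetic is right on its assumptions. But it is a missing operational detail. No two statements conflict, and none is wrong. The concern needs the four months to be counted from a later event that the protocol never names. The Overview also refers to a flow chart of the design that is not shown here and may give the timing, so absence from the visible text is weak evidence. On T3, the Abstract defines the long-term effect as the change from baseline to 8 months, so that comparison does not require a contact-free stretch of fixed length.

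**Conclusion.** The concern does not hold. Counting T2 from baseline in both arms is the sound choice: baseline precedes randomization, so a delay in starting contacts cannot shift the outcome visit in one arm relative to the other. On the ordinary reading, contacts fill the interval from T1 to T2, and following the plan as written gives a valid 4-month comparison. Because eight is a maximum, a dyad with fewer contacts by T2 is within the protocol.

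The 15-day margin assumes evenly spaced contacts at the control arm's pace; under the other spacings tried it runs from 0 to about 73 days. The document shows no wait longer than any of these. Any loss of effect would require both a late start and an effect that grows with the number of contacts. Its size cannot be derived from the protocol and may be zero. A sentence naming the start of the contact period would be tidy, but nothing in the primary result depends on it.

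### Does the protocol need a rule on who answers the NPI, and on when it is asked, because only the interviewers are masked?

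*Protocol*

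**What the plan says.** The primary aim in Section 5 is the NPI total score at 4 months (T2). On masking, the Overview in Section 6 says only: "Interviewers will be masked to treatment assignment throughout the study (Figure 1". The NPI informant is not named. The Overview describes the population as "Veterans with dementia whose caregivers report one or more NPS", and the caregiver eligibility criteria again make the caregiver the source of the symptom report.

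The arms look different to a participant. TAP-VA is delivered by an occupational therapist in the home, whereas "caregivers in the attention control group will receive bi-monthly telephone contact (up to 8 contacts". The control contacts also cover the value of activity and supply activity ideas. Under Recruitment Procedures, the baseline interview takes place "prior to randomization to study group".

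The Eligibility Criteria require a caregiver to "self-identify as the primary member of the family caring (hands-on or supervision) for the Veteran". If more than one caregiver wishes to join, the team "will obtain informed consent from each caregiver and will work with them as a caregiving unit". Secondary aim 2 measures "caregiver burden, skill acquisition, efficacy using activities, and time spent providing care" at 4 and 8 months in both arms. Secondary aim 3 is to "Examine whether caregivers receiving TAP-VA are using activities at 8 months".

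**The concern.** The likely informant for the primary outcome also receives the treatment, and the Techniques text says caregivers are helped to rethink their expectations and reactions. Interviewer masking cannot remove reporting bias from that source. Two further gaps look avoidable.

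- **Respondent.** Where several caregivers take part, one might answer at baseline and another at 4 months. That would add rater noise to the primary comparison and blur whose burden, skill and time are being measured.
- **Order.** If skill and efficacy questions come before the NPI, the answers could hint at the arm and weaken the only masking the protocol has.

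A baseline from someone who was never interviewed at baseline cannot be recovered later, so a written rule looks like cheap insurance.

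**Working it through.** **1. Caregiver masking.** The protocol gives no size or direction for reporting bias, so any figure is an illustration. Take 80 dyads per arm (1:1 assumed), two-sided alpha 0.05, no true effect, and a reporting shift of b SD. The chance of a significant result is P(|Z + b/√(2/80)| > 1.96), with √(2/80) = 0.158.

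- b = 0.2: shift 0.2/0.158 = 1.26, probability about 24%.
- b = 0.3: shift 0.3/0.158 = 1.90, probability about 47%.

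These are large, but neither a respondent rule nor an item order would change them. They describe a limit of any trial of caregiver training with a caregiver-reported outcome. The attention control and the pre-randomization baseline are the available safeguards, and both are in place.

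**2. Who the respondent is.** The caregiver criteria, read together, describe a self-identified primary family caregiver who lives with the Veteran, reports the symptoms, can be reached for follow-up interviews and expects to stay in the area for 8 months. Dyads are randomized and retested. The sentence on caregiving units concerns consent and participation; it does not say that respondents may rotate. The default is therefore clear, though not written as an assessment rule.

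**3. What a change of respondent would cost.** Assumptions (none from the protocol): T1–T2 correlation 0.6 with the same respondent and 0.4 with a different one, equal variances, and no mean difference between respondents. Residual variance is 1 − r², so 0.64 and 0.84. With share f of dyads affected, the average is 0.64(1 − f) + 0.84f, and effective N = 160 × 0.64 / average.

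| f | Average residual variance | Increase | Effective N | Dyads lost |
|---|---|---|---|---|
| 10% | 0.66 | 3.1% | 155.2 | 4.8 |
| 20% | 0.68 | 6.3% | 150.6 | 9.4 |
| 30% | 0.70 | 9.4% | 146.3 | 13.7 |

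The detectable difference grows with the square root of the variance: √1.031 = 1.016, √1.063 = 1.031, √1.094 = 1.046, or 2% to 5%. At the planned accrual of 160/33 = 4.85 dyads per month, the loss equals 1.0, 1.9 or 2.8 months of recruitment.

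**4. What a strict rule would cost.** Suppose the primary caregiver must be the sole respondent, and that changes occur because this person is unavailable. The outcome is then missing in 0.10 × 160 = 16, 0.20 × 160 = 32 or 0.30 × 160 = 48 dyads. Accepting a substitute costs 4.8/16 = 0.30, 9.4/32 = 0.29 or 13.7/48 = 0.29 of a dyad for each change; a missing answer costs a whole dyad. Unavailability may also be related to outcome. The strict rule gains only where the primary caregiver was available and someone else answered.

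**5. Item order.** No order is stated, so no poor order has been fixed. The skill items are asked in both arms, and controls also receive activity ideas, which dulls any hint. Placing the NPI first would shield it at T2. However, skill items asked later in that interview could still reveal the arm before the T3 NPI, and Section 2 lists only one person in the interviewer role. An allocation guess recorded straight after the NPI would miss unmasking by those later items.

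**The case for a change.** The best case for a change is that the protocol creates the ambiguity itself. It admits several caregivers per Veteran into a trial built on dyads and does not say who answers. The primary-caregiver criterion governs enrolment, not assessment. An analysis plan cannot supply a baseline that was never collected, and a few sentences would settle the matter.

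Part of this stands. No sentence in the text shown names the NPI respondent, and a change between visits cannot be fully undone. But respondent changes can be examined in a sensitivity analysis if the respondent's identity is recorded, as a competent field team would do. The text shown is also incomplete on this subject. The Overview promises fuller description of each component, and Recruitment Procedures points to data analytic considerations; neither a measures section nor those considerations appear. A respondent or order rule may sit there or in an interviewer manual, so its absence here is weak evidence that none exists.

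**Conclusion.** No change to the plan is needed. The masking statement is sound, and unmasked caregiver reporting is inherent in the design and should be acknowledged when results are interpreted. The respondent gap is one that a team following the protocol would fill sensibly: interview the primary caregiver at each visit and note any substitute. If it were filled less well, the harm is mainly lost precision: about 5 to 14 effective dyads of 160, or a detectable difference 2% to 5% larger. That rests on assumed correlations of 0.6 and 0.4 and assumed changes in 10% to 30% of dyads; the protocol gives no figure for either. A sole-respondent rule is a debatable trade-off that could lose more than it saves, and item order is an interviewing precaution with only partial effect at 8 months.
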